4.4.1 Permitted Therapy

Participants are eligible for study participation whether or not they are receiving approved medication for AD (i.e., acetylcholinesterase inhibitors, memantine, and/or medical food supplements, where approved) with the exception of GV-971. Participants who are receiving GV-971 or who are planning to receive GV-971 during the study are not eligible. Information about background AD medication (e.g., drug name, dose, and start and stop dates, reason for interruption or modification) has to be captured on eCRF. Randomization will be stratified for participants taking and not taking approved anti-dementia medications.

Adding a new medication or changing the dose of a medication after randomization should occur only for the treatment of an adverse event or in case of AD progression. Whenever possible, a medication listed below should be used if appropriate.

The following medications are permitted if the dose and dose regimen have been stable for at least 3 months prior to screening and are expected to remain stable after screening or if required for treatment of an adverse event after randomization:

- Anticonvulsant medications for an approved pain indication
- Selective serotonin reuptake inhibitors for the treatment of depressive symptoms
- Over-the-counter and/or herbal medications, food additive, or any other agent or supplement intended to improve cognition or reduce cognitive decline
- Medications used to treat a mood or anxiety disorder given as maintenance treatment (with the exception of benzodiazepine)
- Intermittent use of short-acting (non-extended release) opioid medications for pain except within 2 days or 5 half-lives (whichever is the longer) of any cognitive assessment (up to a maximum of 3 consecutive days per month)
- Intermittent use of benzodiazepines, including alprazolam, lorazepam, oxazepam, triazolam, or temazepam, or a one-time dose of diazepam or a short-acting hypnotic medication (e.g., zolpidem) if use is intermittent for sleep or anxiety, except within 2 days or 5 half-lives (whichever is the longer) prior to any cognitive assessment
- A dose of benzodiazepine for pre-surgical and pre-imaging sedation at appropriate visits if allowed by the EC or IRB

- Intermittent use of centrally acting antihistamine medications except within 2 days or 5 half-lives (whichever is the longer) prior to any cognitive assessment
- Under certain circumstances, initiation of anti-hemostasis medications during the study conduct

Anticoagulation therapy lasting no longer than 3 weeks (e.g., temporary usage during surgery) is permitted. Nevertheless, *anticoagulation therapy may require temporary study drug interruption and advice from the Medical Monitor is recommended.*

Concomitant and excluded therapies for determination of participant eligibility are described in Section [4.1.2.7](#).

Participants who use oral contraceptives, hormone-replacement therapy, or other maintenance therapy should continue their use.

4.4.2 Prohibited Therapy

Any medication that is prohibited before screening is also prohibited during conduct of the study (see Section [4.1.2.7](#)). If a participant receives any prohibited treatment during the study, the participant may be withdrawn from study treatment.

4.5 STUDY ASSESSMENTS

Refer to [Appendix 1](#) for the schedule of activities to be performed during the study.

At applicable sites, certain study assessments may be performed by a home nursing (HN) professional at the participant's home or nursing center to improve access and convenience for participants participating in the study. The Sponsor has selected a healthcare company that is responsible for providing HN services for participating sites (the HN vendor). The HN vendor is responsible for ensuring that all HN professionals are licensed, qualified, and in good standing, as per applicable regulations, and that appropriate background checks have been performed. If the investigator at a participating site determines that HN services are appropriate for a participant and the participant gives written informed consent to participate in HN visits, the HN network communicates with the participant and the participant's site. HN visits are scheduled on specified visit days to allow relevant assessments to be performed by the HN professional. The schedule of activities (see [Appendix 1](#)) specifies which assessments may be performed by an HN professional.

4.5.1 Informed Consent Forms and Screening Log

All participants and study partners must review, sign, and date the most current IRB/EC-approved written informed consent for participation in the study before any study-specific prescreening assessments, screening tests or evaluation are performed. Informed Consent Forms for enrolled participants and their study partners and for those who are not subsequently enrolled will be maintained at the study site.

All prescreening and screening evaluations must be completed and reviewed to confirm that participants meet all eligibility criteria before randomization. The investigator will maintain a screening log to record details of all participants prescreened and screened and to confirm eligibility or record reasons for screening failure, as applicable. Prescreening is optional and is covered by a dedicated Informed Consent Form.

4.5.2 Medical History, Concomitant Medication, and Demographic Data

Medical history includes clinically significant diseases, surgeries, cancer history (including prior cancer therapies and procedures), smoking history, use of alcohol, and drugs of abuse. In addition, all medications (e.g., prescription drugs, over-the-counter drugs, herbal or homeopathic remedies, nutritional supplements) used by the participant within 3 months prior to screening visit will be recorded. Demographic data will include age, sex, and self-reported race/ethnicity. Medical history and demographic data will be collected at the screening visit only.

As this study is being conducted in multiple geographic regions, it is likely that participants of different ethnic origins will be enrolled in the study. Although there is currently no indication that gantenerumab is metabolized or eliminated differently or that the treatment effect would be different in participants of different ethnic origins, collecting this information is essential to adequately evaluate the results of this study (e.g., possible differences in PK exposure [concentration of the drug in the blood] or treatment effect).

4.5.3 Physical Examinations

A complete physical examination should include an evaluation of the head, eyes, ears, nose, and throat, and the cardiovascular, dermatological, musculoskeletal, respiratory, gastrointestinal, genitourinary (optional), and neurological systems. Any abnormality identified at baseline should be recorded on the General Medical History and Baseline Conditions eCRF.

The schedule of activities indicates when complete physical examinations (including neurological systems) are to be recorded (see [Appendix 1](#)).

Limited, symptom-directed physical examinations should be performed per the schedule of activities (or as clinically indicated). Changes from baseline abnormalities should be recorded in participant notes. New or worsened clinically significant abnormalities should be recorded as adverse events on the Adverse Event eCRF.

In addition, weight will be obtained at screening, and at every visit at which creatinine clearance is tested as well as at any other visit as deemed necessary by the investigator. Height will be obtained at screening only.

4.5.4 Vital Signs

Vital signs will include measurements of pulse rate and systolic and diastolic blood pressure. Blood pressure and pulse rate should be taken when the participant is at rest and should not be measured unless at least 15 minutes have elapsed since the last blood draw. The same arm should be used for all blood pressure measurements.

Pulse rate will be determined and will be recorded as beats per minute. If obtained manually, the pulse rate should be counted for a minimum of 20 seconds at each assessment.

Vital sign measurements may be performed by an HN professional.

The schedule of activities indicates when vital signs (blood pressure and pulse rate) are to be recorded (see [Appendix 1](#)).

4.5.5 Cognitive, Functional, and Health Economics Assessments

The assessments described in this section will be performed as outlined in the schedule of activities (see [Appendix 1](#)) and in the order specified in Section 4.6.

Whenever possible, there should be consistency in the rater and study partner who complete the scales for each participant throughout the duration of the study. Potential raters will receive training and be approved by the rating scale contract research organization (CRO) prior to being allowed to administer any cognitive assessments or rating scales in the study.

Whenever possible, cognitive and functional assessments should be performed at the visit timepoints indicated in the schedule of activities (see [Appendix 1](#)). However, in exceptional circumstances for post-randomization visits, if the caregiver, the primary rater, or even the participant cannot perform these assessments as per the schedule of activities, they may be performed up to 4 weeks out of window.

Given that the primary outcome measure in this trial involves subjective judgment, the adequacy of participant and study partner interviews and ratings will be monitored by an endpoint reliability program administered by the rating scale vendor; this is considered an essential part of good research methodology. For the primary endpoint as well as for some other scales, audio recordings may be used for quality assurance purposes. Prior studies have clearly demonstrated that the failure to adequately monitor such ratings can substantially increase the risks of failed trials (Becker and Greig 2008; Kobak 2010).

4.5.5.1 Clinical Dementia Rating Scale

The CDR global score (CDR-GS) characterizes a participant's level of impairment according to the following categories: 0 (normal), 0.5 (very mild dementia), 1 (mild dementia), 2 (moderate dementia), and 3 (severe dementia). The SOB score is a detailed quantitative general index that provides more information than the CDR-GS in

participants with mild dementia (Berg 1988; Morris et al. 2001, O'Bryant et al. 2010) and is scored from 0–18 with higher scores indicating greater impairment. The CDR characterizes six domains: memory, orientation, judgment and problem solving, community affairs, home and hobbies, and personal care. The necessary information to make each rating is obtained through a semi-structured interview with the participant and a reliable informant or collateral source (e.g., a study partner).

As much as is feasible, the CDR should be administered to an individual participant by the same assessor throughout the study and that assessor should not perform the MMSE, ADAS-Cog, Verbal Fluency Task, Coding, FAQ, or Alzheimer's Disease Cooperative Study Group–Activities of Daily Living (ADCS-ADL). However, if in exceptional circumstances only this assessor is available to perform these other scales, then the CDR participant interview must be completed after the study partner interview but before ADAS-Cog, MMSE, Verbal Fluency Task, Coding, and other scales are completed. Nevertheless, at screening, baseline, Week 104, Week 116 or Week 128 (if applicable), the CDR rater cannot perform other scales than the CDR. In addition, the CDR rater should not be involved in safety assessments and especially should not receive information about any ARIA findings.

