Gantenerumab will be administered by SC injection to all patients randomized to the active treatment arm, regardless of *APOE* ε4 status, at a dose of 120 mg SC Q4W for 3 months, 255 mg SC Q4W for 3 months, and 510 mg SC Q4W for 3 months, prior to reaching the target dose. Once the target dose is reached, study drug will be administered every 2 weeks (Q2W administration of 510 mg SC gantenerumab). The switch to a Q2W administration schedule allows decreasing the number of SC administrations in the abdomen per visit.

Note: A minimum of 3 doses during each dosing step must be administered prior to up-titration.

For Q4W injections, a time window of ± 7 days is allowed for dosing visits. For Q4W injections, the recommended minimum time between doses is 3 weeks. The maximum recommended time between doses should not exceed 6 weeks. Once study drug is administered Q2W, the time window for dosing visits is ± 3 days. For Q2W injections, the recommendation is not to administer more than 1020 mg (i.e., 2 times 510 mg Q2W) within 28 days. Always return to the initial planned schedule per randomization for subsequent visits.

Regardless of dose, each participant will undergo up to a total of 49 dosing visits in scenario 1 or 55 dosing visits in scenario 2 (if applicable) in the double-blind treatment period of the study. Participants who have completed the double-blind treatment period at the time of the implementation of *the 12 week study extension*, will have undergone up to 43 dosing visits. Injections will be administered as one 0.8-mL (120-mg dose), one 1.7-mL (255-mg dose), or two 1.7-mL injections (510-mg dose) subcutaneously to the abdomen, respectively.

Placebo of identical composition (except protein) and identical volume to gantenerumab will be administered by SC injection to all participants randomized to placebo at the same frequency and using the same route of administration.

On study drug administration days that include efficacy assessments, study drug must be administered at the clinical site. Study personnel preparing and administering study drug must not be involved with any efficacy assessments or safety evaluations.

At applicable sites, study drug may be administered by a trained nursing professional at the participant's home or another suitable location, if the participant has given written informed consent to participate in home nursing visits.

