1.2.3 Safety Overview

Nonclinical characterization of gantenerumab did not show any relevant safety findings. To date, ARIAs and ISRs are the identified risks for gantenerumab. No differences between active and placebo groups have been observed in laboratory parameters, physical and neurological examinations, vital signs, or electrocardiogram (ECG) parameters.

Amyloid-Related Imaging Abnormalities

In the double-blind phase of Study WN25203 (prodromal AD), ARIA events were time, dose, and *APOE* ϵ 4 allele status dependent. The incidence of ARIA-E was 0.8% in the placebo, 6.6% in the 105-mg gantenerumab, and 13.5% in the 225-mg gantenerumab groups. For ARIA-H, the incidence was 13.2% in the placebo, and 22.9% and 16.2% in the 105-mg and 225-mg gantenerumab treatment groups, respectively. The rates of new ARIA-E were highest between 3 and 6 months of treatment (3.8% and 7.5% in the 105-mg and 225-mg gantenerumab groups, respectively) and decreased substantially after

the first year of treatment (incidence of up to 2.3% in the 225-mg gantenerumab group in approximately 2 years). The median MRI Barkhof grand total score (BGTS) (Barkhof et al. 2013) of these findings was 3. Most ARIA events were asymptomatic and did not lead to clinically significant consequences. A total of 5 patients (1.8%) from the 105-mg gantenerumab arm and 6 patients (2.3%) from the 225-mg gantenerumab arm experienced symptoms related to ARIA findings; the most commonly reported symptom was headache (5 patients). Other symptoms reported with ARIA-E included visual disturbances (left eye diplopia and upper left quadrantanopia), focal seizure (dysarthria/aphasia that lasted for 10 minutes), anxiety, hyperreflexia, confusional state, disturbance in attention, cognitive disorder, malaise, and dizziness. Symptomatic ARIAs were of mild severity and were non-serious except for one serious adverse event of focal seizure.

Following the futility analysis for Study WN25203, treatment in the double-blind phase was discontinued in July 2017 (median double-blind treatment duration: 68 weeks) and consenting patients transitioned into OLE.

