Thus, based on the information from the WN25203 and WN28745 OLE studies, in which gantenerumab (manufactured with G3 process) up to 1200 mg Q4W was assessed and shown to be safe for *APOE* ϵ 4 allele carriers and non-carriers, and based on the internally developed PK-PD models, the following dosing regimen for Study WN29922 was selected: 150 mg Q4W for 3 months, then 300 mg Q4W for 3 months, and then 600 mg Q4W for 3 months, followed by 600 mg Q2W until the end of the study. The switch to a Q2W administration schedule allows patients to decrease the number of SC administrations in the abdomen per visit.

The PK-PD models referenced above were developed based on information from the G3 material and were used to establish the initial dosing regimen for this study. As indicated previously, gantenerumab drug substance manufacturing process was optimized from G3 to G4, and a relative bioavailability study (WP40052) assessed the pharmacokinetic difference between the G3 and G4 material in humans.

The results of this relative bioavailability study (WP40052) show that the AUC_{inf} is approximately 1.18 fold and the C_{max} is approximately 1.05 fold higher after administration of G4 compared with G3. As AUC is considered the driver of the treatment effect, the conversion factor of 1.18 from the G3 to G4 material has been based on the AUC_{inf} . The association between microglial-driven removal of aggregated brain amyloid and AUC has been shown in preclinical experiments and clinical studies. In addition, as gantenerumab exhibits linear pharmacokinetics, the AUC_{inf} after single dose reflects the steady state exposure (AUC_{tau}) after multiple doses.

Based on the above rationale and the fact that gantenerumab manufactured with G4 process was safe and well tolerated, the G3 dosing regimen has been converted into the following G4 dosing regimen for the WN29922 study: 120 mg Q4W for 3 months, then 255 mg Q4W for 3 months, and then 510 mg Q4W for 3 months, followed by 510 mg Q2W until the end of the study. This schedule enables titration to target dose within 9 months (see [Table 1](#)), with predicted overall ARIA-E rate of approximately 26% based on the current ARIA-E hazard model. The low starting doses and gradual increase in dosing (i.e., slow titration schedule) are expected to reduce the risk of ARIA-E for both

APOE carriers and non-carriers. An MRI scan, confirming the absence of ARIA-E findings, will be required prior to each dose increase.

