4.6.5 Procedures for New MRI Findings

In addition to any local reading according to local procedures and requirements, all MRI scans will be reviewed by an expert central reader within approximately 1 week of receipt and a report provided to the site. For the purposes of overall study relevant decisions and recommendations, including participant eligibility as well as for analysis, results from the expert central reader will be used. Any time the central reader identifies a new MRI finding the study center medical staff and the Sponsor will be rapidly notified (see Section [4.5.9](#)).

Refer to Section [5.1.2](#) for instructions in the event of new MRI findings (ARIA-E and ARIA-H).

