The efficacy analyses will be based on the ITT analysis set (see [Table 2](#)) and will compare the active drug arm against the placebo arm with regards to mean change from baseline to Week 116. Two-sided test hypotheses will be defined in the following sections and the type I error level will be 5%. There are two identical Phase III studies, for each respective study the type I error level will be 5%. In order to protect the overall type I error rate (i.e., at each study level) when incorporating the hypothesis testing of multiple endpoints into the analysis, a fixed sequence testing procedure ([Westfall and Krishen 2001](#)) will be used to adjust for multiple comparisons. Testing of each hypothesis will follow a pre-specified order such that an endpoint would only be tested if the preceding one in the hierarchy was significant at 5% alpha level. The endpoint hierarchy, starting with the primary endpoint and including only confirmatory secondary endpoints, is the following:

1. CDR-SB (Clinical Dementia Rating, Sum of Boxes)
2. ADAS-Cog 13 (Alzheimer's Disease Assessment Scale, Cognitive subscale, 13-item)
3. ADCS-ADL (Alzheimer's Disease Cooperative Study, Activities of Daily Living scale) total score
4. FAQ (Functional Activities Questionnaire)

Missing outcome data will be handled using data imputation aligned with the estimand, see Section [5.3.3](#) for a detailed description of the analysis strategy.

When using a statistical model with baseline covariate adjustment, missing baseline covariate data other than the baseline outcome measure will be imputed to the overall median value for continuous covariates, or will be imputed to the most frequent category for categorical variables. In addition, baseline covariates will be derived from information collected into the eCRF, unless otherwise specified.

In statistical models using change from baseline of a given outcome measure as the dependent variable, there will be no imputation of the baseline outcome value, with the consequence that participants missing the baseline outcome measure will not contribute to the analysis.

The impact of the COVID-19 pandemic on the study and its conduct will be monitored and the overall impact will be assessed and described in the Clinical Study Reports.

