#### **5.4 SECONDARY ENDPOINTS ANALYSES**

The same primary estimand's analysis strategy (see Section 5.3.2) will be applied to secondary endpoints listed in Table 5, with the following exceptions for the corresponding estimator:

- *. the imputation model will not include, as covariates, the baseline ADAS-Cog 13 total score and the baseline ADCS-ADL total score*

*The imputation model will thus include treatment group, visit, and treatment-by-visit interaction, the baseline score and the baseline score-by-visit interaction, and the randomization stratification factors, namely: disease stage, geographic region, the use of AD medication at baseline and the APOE ε4 status*

- *the analysis model will not include, as covariates, the baseline ADAS-Cog 13 total score and the baseline ADCS-ADL total score*

*The analysis model will thus include treatment, the baseline score and the randomization stratification factors, namely: disease stage, geographic region, the use of AD medication at baseline and the APOE ε4 status*

In the following, confirmatory secondary endpoints refer to endpoints included in the type I error control procedure. Other important secondary endpoints not subject to the type I error control procedure are considered as supportive secondary endpoints. For all secondary endpoints, the treatment effect over time will also be considered and the change from baseline to Weeks 24, 52, 76, and 104 will be provided as supplementary analyses.

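### The rule that keeps ARIA findings from the CDR rater does not extend to whoever rates ADAS-Cog 13, ADCS-ADL and FAQ, the three confirmatory secondary endpoints

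*Protocol*

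**What the plan says.** **The protected rater.** Protocol 4.5.5.1 states that "the CDR rater should not be involved in safety assessments and especially should not receive information about any ARIA findings". The same paragraph adds that at screening, baseline, Week 104 and the final visit "the CDR rater cannot perform other scales than the CDR".

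**The other raters.** Protocol 4.5.5.2 (ADAS-Cog), 4.5.5.7 (FAQ) and 4.5.5.8 (ADCS-ADL) contain no blinding rule. Section 4.5.5 asks for rater training, approval, consistency and quality monitoring; none of these limits access to safety data.

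**The other separation of staff.** Protocol 4.3.2.1: "Study personnel preparing and administering study drug must not be involved with any efficacy assessments or safety evaluations". This covers the people who handle or inject drug.

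**Where ARIA information goes.** When the central reader finds something new on MRI, "the study center medical staff and the Sponsor will be rapidly notified" (Protocol 4.6.5). Results must reach investigators before the next dose (4.5.9), and the investigator must review every ARIA finding (5.3.5.1). None of these sections makes an exception for raters.

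**Status of the scales.** SAP 5.4 explains that "confirmatory secondary endpoints refer to endpoints included in the type I error control procedure". SAP 5.1 lists them after CDR-SB as ADAS-Cog 13, ADCS-ADL total score and FAQ.

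**Planned ARIA-E analysis.** SAP 5.3.5.2 sets post-ARIA-E data to missing and imputes them under MAR, for the primary endpoint only.

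**The concern.** ARIA-E is rare on placebo and common on this antibody, so a rater who learns of one can guess the arm. The protocol recognises this for CDR. It then assigns the confirmatory secondary scales at Week 116 to a person whom the ARIA rule does not name. As written, the staff member who reads the MRI report and follows the dose hold may also administer ADAS-Cog 13 and take ADCS-ADL and FAQ from the study partner.

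At stake is how far these endpoints corroborate the primary. SAP 5.4.1 says they are there to add confidence to the CDR-SB effect. If their rater can infer the arm for a sizeable group of active participants, a favourable ADAS-Cog 13 result is open to a rater-expectation explanation that was guarded against for CDR.

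**Working it through.** **1. The protocol's ARIA-E rate.** Protocol 1.3.2 gives the regimen "with predicted overall ARIA-E rate of approximately 26% based on the current ARIA-E hazard model". It can be rebuilt:

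- Concentrations: the two-compartment SC model of Appendix 4 Table 1, bioavailability multiplied by 1.18 for G4 material (1.3.2), with the short zero-order absorption step ignored.
- Regimen: 120, 255 and 510 mg Q4W, three doses each, then 510 mg Q2W, over 104 weeks.
- Hazard: baseline × exp[Emax·c/(c+EC50) × ET50^γ/(ET50^γ+t^γ)], with Appendix 5 Table 9 values (baseline 2.14E-5 per day for non-carriers and 3.52E-5 for carriers, Emax 5.92, EC50 6.78 µg/mL, ET50 323.44 days, γ 2.15).
- Result: 19.2% in non-carriers and 29.6% in carriers. The documents do not give this trial's carrier share. Assuming 50% to 75%, the overall rate is 24.4% to 27.0%; at 65% it is 26.0%. The stated 26% reproduces.

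**2. Placebo rates.** Study WN25203: "The incidence of ARIA-E was 0.8% in the placebo" group. Study WN28745: 1.5%. Both are in Protocol 1.2.3.

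**3. Probability of active given a known ARIA-E.** With 1:1 allocation (Protocol 3.1.1), P = p_active / (p_active + p_placebo).

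| Active rate | Placebo rate | P(active given ARIA-E) |
|---|---|---|
| 26% (predicted, this trial) | 0.8% | 26/26.8 = 97.0% |
| 26% (predicted, this trial) | 1.5% | 26/27.5 = 94.5% |
| 13.5% (WN25203, 225 mg) | 0.8% | 13.5/14.3 = 94.4% |
| 6.6% (WN25203, 105 mg) | 0.8% | 6.6/7.4 = 89.2% |
| 11.5% (WN28745) | 1.5% | 11.5/13.0 = 88.5% |

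The first two rows pair a model prediction with placebo rates from other studies. The last three are within-study double-blind comparisons at lower doses. Protocol 1.2.2.3 gives 9.4% instead of 11.5% for WN28745 active; that gives 9.4/10.9 = 86.2%. Replacing the prediction by the open-label rates at higher dose (30.5% and 32.4%, Protocol 1.2.3) gives 30.5/32.0 = 95.3% to 32.4/33.2 = 97.6%.

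**4. How many participants.** With 508 per arm: 0.26 × 508 ≈ 132 on active, against 0.008 × 508 ≈ 4 to 0.015 × 508 ≈ 8 on placebo.

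**5. The converse.** Absence of ARIA-E says little. P(placebo given none) = 0.992/(0.992+0.740) = 57.3%, or 0.985/(0.985+0.740) = 57.1%.

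**6. Who rates at Week 116.** The CDR rater may not do the other scales. The drug-handling staff may not do any efficacy scale. No rule on access to ARIA findings applies to whoever remains.

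**The case against.** **The scales differ in kind.** Protocol 4.5.5 links its monitoring programme to the subjective judgment in the primary measure. ADAS-Cog is a participant test scored on errors (SAP 5.4.1.1), while ADCS-ADL and FAQ are informant-based. Rater discretion is therefore smaller than for CDR. This stands in part. A likelier route of bias for ADCS-ADL and FAQ is the study partner, who may know of extra scans or a dose hold, and a rater rule does not reach that. But CDR also depends on study-partner input, and its rater was still shielded. ADAS-Cog 13 remains the scale where such a rule helps most.

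**Gatekeeping.** A reader might infer that this gap could turn a failed trial into a positive one. It cannot: the secondaries are tested only if CDR-SB is significant, and CDR-SB has the shielded rater.

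**Size in scale points.** A reader might want the bias in ADAS-Cog points. The documents give no basis for how far an informed rater would shift a score, and no standard deviation or target effect against which to judge a shift.

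**Injection-site reactions.** A reader might add these as a second unblinding signal of equal strength. The high rates in the protocol come from open-label treatment and cannot fairly be set against double-blind placebo rates. Drug-administering staff are also already kept out of efficacy work. ARIA-E carries the point alone.

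**Silence is not proof.** A rater manual or the rating-scale vendor's materials may contain such a rule. Neither document cites one, and nothing here shows that any rater has received ARIA information.

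**Staffing.** A hard ban could force a fourth separate role at small sites among about 175 centers. This stands, and it argues for a feasibility clause.

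**Conclusion.** The point holds as a gap in bias protection for the confirmatory secondaries. For the roughly quarter of active participants expected to have ARIA-E, knowing of it implies the active arm with probability about 94.5% to 97%, or 88.5% to 94.4% on the within-study lower-dose figures. These percentages are derived, not stated in the documents. They rest on the predicted 26%, on placebo rates carried over from earlier studies, and on the rater actually learning of the finding. They do not describe participants without ARIA-E.

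The consequence is weaker corroboration of a CDR-SB result, chiefly from ADAS-Cog 13 and only partly from ADCS-ADL and FAQ. The primary test and its type I error are not affected by this gap.

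A reader might also take the ban at baseline, Week 104 and Week 116 as a visit-specific ARIA rule for CDR that could be copied. It is not: that ban governs performing other scales, while the ARIA sentence is a general recommendation without visit tiers. A special requirement at baseline would serve little purpose, since no on-treatment ARIA exists then and ARIA-E on the screening MRI excludes entry (Protocol 4.1.2.2).

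**What to change.** **Protocol 4.5.5.1.** Widen the subject of the existing sentence from the CDR rater to the raters of the CDR and, as far as feasible, of the ADAS-Cog, ADCS-ADL and FAQ. Leave its recommendation on safety work and ARIA findings otherwise unchanged, and add a line to rater training.

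*Cost:* some sites must reassign who rates and who handles safety. The feasibility clause means that no extra staff are required.

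**SAP 5.3.5.2.** Version 3 of the SAP follows a version dated 29 July 2022, so many assessments are probably complete and new rater wording cannot reach them. For those, repeat the ARIA-E supplementary analysis for ADAS-Cog 13, ADCS-ADL total score and FAQ.

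*Cost:* three further runs of a method already specified. *Limits:* it relies on MAR after ARIA-E, discards data mostly from the active arm, and cannot separate rater knowledge from any effect of ARIA-E or of the dose interruption that may follow. It should be read as a robustness check.

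Neither change touches dosing or ARIA management.
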